## 2. Study objectives

### Primary Objective

- To measure grade 3-5 toxicity of regorafenib in older adults with mCRC with implementation of focused education and support initiatives

### Secondary Objectives

- To evaluate efficacy of regorafenib in older adults with mCRC (RR, PFS, DCR and OS)
- To explore association between baseline CGA findings and risk of toxicities
- To explore the association of toxicities with CGA domain changes over time
- To assess patient-reported QOL on regorafenib over time

## 4. Study Design

Given 54% grade 3/4 toxicity and required dose modification among 76% of patients in the regorafenib arm (randomized phase III CORRECT trial), we will initiate treatment at a reduced dose of 120mg in this geriatric study population on a similar 3 weeks on/1 week off schedule. Dose escalation to 160mg will be recommended after the first cycle (4 weeks) at the discretion of the treating physician. There is good precedent for starting at reduced doses in similar trials – the FOCUS2 study team utilized 80% starting chemotherapy doses in their study among the elderly with metastatic CRC and dose escalated if tolerated.

Participants will undergo a comprehensive geriatric assessment (CGA) at baseline, at 4 weeks and then every 3 months (+/- 7 days) while on study to assess for any deterioration in geriatric domains (functional status, comorbidities, nutrition, psychological state, social support and cognitive ability). All sites have personnel experienced in performing geriatric assessments and the University of Rochester as the lead site will conduct training to ensure that all sites will conduct the assessments in the same way.

All patients will receive intensive one-on-one education about prevention/management of skin toxicity, diarrhea, fatigue and other toxicities at initiation and follow-up visits (see section 7 & 8 for review of treatment strategies). Starter packs with moisturizing cream (10% urea content), socks and patient-friendly ‘Tips for Skin Care’ will be distributed. On-treatment visits will occur weekly for first two cycles and every 4 weeks after that. Alternate weekly visits may be substituted with a home nursing visit for BP check and symptom evaluation if it is not feasible for patient to attend clinic visits weekly. Pill adherence diaries will be provided to patients and pill counts will be performed at the end of every cycle.

Restaging CT/MRI scans will be completed every 12 weeks (+/- 7 days) (or sooner if treating oncologists suspects progression of disease based on clinical symptoms). Radiographic disease progression is defined by Response Evaluation Criteria in Solid Tumors (RECIST 1.1) (see Appendix A). Subjects will have a Safety Follow-up visit within 30 days after their last dose of study drug or prior to the initiation of another antineoplastic therapy, whichever occurs first. After treatment discontinuation, survival status will be assessed periodically (see Table of Assessments).

## 5. Study Population / Eligibility/Re-Screening

Re-screening may be allowed. Subjects who are re-screened must be consented as if they were a new patient. If a patient re-screens, they will be assigned a new subject ID when entered into Red Cap.

### Inclusion Criteria

- Histologically or cytologically confirmed colorectal adenocarcinoma
- Evidence of measurable (by RECIST criteria) metastatic disease

- Age 65 years or over
- Progression of disease on standard therapy or deemed not a candidate for further chemotherapy by treating oncologist or patient declines other options.
- ECOG PS 0-1
- Life expectancy of at least 3 months.
- Subjects must be able to understand and be willing to sign the written informed consent form. A signed informed consent form must be appropriately obtained prior to the conduct of any trial-specific procedure.
- Adequate bone marrow, kidney and liver function as assessed by the following laboratory requirements:
  - Total bilirubin  $\leq 1.5$  x the upper limits of normal (ULN).
  - Alanine aminotransferase (ALT) and aspartate amino- transferase (AST)  $\leq 2.5$  x ULN ( $\leq 5$  x ULN for subjects with liver involvement of their cancer).
  - Alkaline phosphatase limit  $\leq 2.5$  x ULN ( $\leq 5$  x ULN for subjects with liver involvement of their cancer).
  - Creatinine  $\leq 1.5$  x the ULN.
  - International normalized ratio (INR)/ Partial thromboplastin time (PTT)  $\leq 1.5$  x ULN.

Platelet count  $\geq 100000$  /mm^3, hemoglobin (Hb)  $\geq 9$  g/dL, absolute neutrophil count (ANC)  $\geq 1500$ /mm^3. Blood transfusion to meet the inclusion criteria will not be allowed.
- Subjects (men) of childbearing potential must agree to use adequate contraception beginning at the signing of the ICF until at least 3 months after the last dose of study drug. The definition of adequate contraception will be based on the judgment of the principal investigator or a designated associate.
- Subject must be able to swallow and retain oral medication.

### Exclusion Criteria

- Previous treatment with regorafenib.
- Systemic therapy for metastatic CRC within 28 days of initiating study treatment.
- Previous assignment to treatment during this study. Subjects permanently withdrawn from study participation will not be allowed to re-enter study.
- Uncontrolled hypertension (systolic pressure  $>140$  mm Hg or diastolic pressure  $> 90$  mm Hg [NCI-CTCAE v4.0] on repeated measurement) despite optimal medical management.
- Active or clinically significant cardiac disease including:
  - Congestive heart failure – New York Heart Association (NYHA)  $>$  Class II.

- Active coronary artery disease.
- Cardiac arrhythmias requiring anti-arrhythmic therapy other than beta blockers, calcium channel blockers or digoxin.
- Unstable angina (anginal symptoms at rest), new-onset angina within 3 months before randomization, or myocardial infarction within 6 months before randomization.
- Evidence or history of bleeding diathesis or coagulopathy.
- Any hemorrhage or bleeding event  $\geq$  NCI CTCAE Grade 3 within 4 weeks prior to start of study medication.
- Subjects with thrombotic, embolic, venous, or arterial events, such as cerebrovascular accident (including transient ischemic attacks) deep vein thrombosis or pulmonary embolism within 6 months of informed consent.
- History of other active malignancy within past 2 years (excluding non-melanoma skin cancer).
- Patients with pheochromocytoma.
- Known history of human immunodeficiency virus (HIV) infection or current chronic or active hepatitis B or C infection requiring treatment with antiviral therapy.
- Ongoing infection  $>$  Grade 2 NCI-CTCAE v4.0.
- Symptomatic metastatic brain or meningeal tumors.
- Presence of a non-healing wound, non-healing ulcer, or bone fracture.
- Major surgical procedure or significant traumatic injury within 28 days before start of study medication.
- Renal failure requiring hemo- or peritoneal dialysis.
- Dehydration Grade  $\geq 1$  NCI-CTCAE v4.0.
- Patients with seizure disorder requiring medication.
- Persistent proteinuria  $\geq$  Grade 3 NCI-CTCAE v4.0 ( $> 3.5$  g/24 hrs, measured by urine protein: creatinine ratio on a random urine sample).
- Interstitial lung disease with ongoing signs and symptoms at the time of informed consent.
- Pleural effusion or ascites that causes respiratory compromise ( $\geq$  NCI-CTCAE version 4.0 Grade 2 dyspnea).
- History of organ allograft (including corneal transplant).
- Known or suspected allergy or hypersensitivity to the study drug.
- Any malabsorption condition.

- Any condition which, in the investigator's opinion, makes the subject unsuitable for trial participation.
- Substance abuse, medical, psychological or social conditions that may interfere with the subject's participation in the study or evaluation of the study results.

### **Excluded Therapies and Medications, Previous and Concomitant**

- Concurrent anti-cancer therapy (chemotherapy, radiation therapy, surgery, immunotherapy, biologic therapy, or tumor embolization) other than study treatment (regorafenib) being used for colon cancer.
- Prior use of regorafenib.
- Concurrent use of another investigational drug or device therapy (i.e., outside of study treatment) during, or within 28 days before start of study medication.
- Major surgical procedure, open biopsy, or significant traumatic injury within 28 days before start of study medication.
- Therapeutic anticoagulation with Vitamin-K antagonists (e.g., warfarin) or with heparins and heparinoids.

## **6. Withdrawal of Subjects from Study**

### **Withdrawal**

Subjects **must be withdrawn from the trial** (treatment and procedures) for the following reasons:

- Subject withdraws consent from study treatment and study procedures. A subject must be removed from the trial at his/her own request or at the request of his/her legally acceptable representative. At any time during the trial and without giving reasons, a subject may decline to participate further. The subject will not suffer any disadvantage as a result.
- If, in the investigator's opinion, continuation of the trial would be harmful to the subject's well-being.
- Subject is lost to follow-up.
- Death.

Subjects **may be** withdrawn from the study for the following reasons:

- The subject is non-compliant with study drug, trial procedures, or both; including the use of anti-cancer therapy not prescribed by the study protocol.
- Severe allergic reaction to regorafenib (such as exfoliative erythroderma or Grade 3 or 4 hypersensitivity reaction).
- The development of a second cancer.

- Development of an intercurrent illness or situation which would, in the judgment of the investigator, significantly affect assessments of clinical status and trial endpoints.
- Deterioration of ECOG performance status to 4.
- Use of illicit drugs or other substances that may, in the opinion of the investigator, have a reasonable chance of contributing to toxicity or otherwise skewing trial result.

In all cases, the reason for withdrawal must be recorded in the CRF and in the subject's medical records.

Details for the premature termination of the study as a whole (or components thereof [e.g. centers, dose levels]) are provided in Section 13. Premature Termination of the Study).

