## **7. Treatment[s]**

### **Treatments to be administered**

All patients will receive regorafenib 120mg daily for 3 weeks on and 1 week off with cycle 1. Dose escalation to 160mg will be permitted after the first cycle at the discretion of the treating physician. Subjects will continue study treatment until disease progression or other reasons for removal from treatment (section6).

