Grade 3	Hold until ≤ Grade 2 c	Reduce by 1 dose level	If toxicity remains < Grade 2, dose re-escalation can be considered at the discretion of the treating investigator. If dose is re-escalated and toxicity (≥ Grade 3) recurs, institute permanent dose reduction.
Grade 4	Hold until ≤ Grade 2 c	Reduce by 1 dose level. Permanent discontinuation can be considered at treating investigator's discretion.	

a. NCI-CTCAE = National Cancer Institute - Common Terminology Criteria for Adverse Events, version 4.0  
b. Excludes alopecia, non-refractory nausea/vomiting, non-refractory hypersensitivity, and non-clinically significant and asymptomatic laboratory abnormalities.  
c. If subject is experiencing multiple grade 2 toxicities, treatment can be interrupted at discretion of treating oncologist until toxicities are ≤ grade 1 and then resumed at reduced dose (by 1 level)  
d. If no recovery after a 4 week delay, treatment should be permanently discontinued unless subject is deriving clinical benefit.

In addition to these recommended dose modifications, subjects who develop diarrhea, mucositis, anorexia or other events predisposing to fluid loss or inadequate fluid intake should be carefully monitored and rehydrated as clinically necessary in order to minimize the risk of postural hypotension and renal failure.

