**Table 8-2 Recommended dose modification for hand-foot-skin reactiona**

Grade of event (NCI-CTCAE v4.0)	Occurrence	Suggested Dose Modification
Grade 1	Any	Maintain dose level and reinforce supportive measures for symptomatic relief
Grade 2	1 st occurrence	Interrupt therapy until toxicity resolves to Grade 0-1. b, c When resuming treatment, treat at reduced dose level.
	2 nd occurrence	Interrupt therapy until toxicity resolves to Grade 0-1. b, c When resuming treatment, treat at reduced dose level.
	3 rd occurrence	Discontinue therapy
Grade 3	1 st occurrence	Interrupt therapy for a minimum of 7 days until toxicity resolves to Grade 0-1. c When resuming treatment, decrease dose by one dose level. b, d
	2 nd occurrence	Discontinue treatment permanently

a. More conservative management is allowed if judged medically appropriate by the investigator.  
b. If toxicity returns to Grade 0-1 after dose reduction, dose re-escalation is permitted at the discretion of the investigator if subject has completed one cycle at reduced dose without recurrence of event.  
c. If there is no recovery after a 4-week delay, treatment with regorafenib will be discontinued permanently.  
d. Subjects requiring > 2 dose reductions should go off protocol therapy.  
e. The maximum daily dose is 160 mg.

**At first occurrence of HFSR, independent of grade, prompt reinforcement of supportive measures such as topical emollients, low potency steroids, or urea-containing creams should be administered.**

Recommended prevention/management strategies for skin toxicities consistent with HFSR are summarized below:

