### Reasons for Follow-up Termination

Patients will remain in the follow-up period until any of the reasons below are satisfied:

- Completion of the study
- Patient death
- Patient withdraws consent from the follow-up period
- Patient is lost-to follow-up

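### Section 6 does not separate stopping regorafenib from leaving the study, so patients removed under it fall between contradictory follow-up rules

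*Combined protocol and SAP*

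**What the plan says.** Section 6 (Withdrawal) has two lists. The mandatory one takes the subject out of the trial, and its lead-in ends "treatment and procedures) for the following reasons". Alongside withdrawal of consent, loss to follow-up and death, it includes the case where, in the investigator's opinion, "continuation of the trial would be harmful to the" subject. The optional list says subjects may be withdrawn from the study. It covers non-compliance, second cancer, intercurrent illness, deterioration to ECOG 4, illicit substance use and "Severe allergic reaction to regorafenib (such as exfoliative erythroderma or Grade 3 or 4 hypersensitivity reaction".

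Section 7 (Treatments to be administered) then uses Section 6 for a different purpose: "Subjects will continue study treatment until disease progression or other reasons for removal from treatment (section6".

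Other sections keep patients under observation after the drug is stopped. Section 4 states: "Subjects will have a Safety Follow-up visit within 30 days after their last dose of study drug", or before another antineoplastic therapy starts if that is sooner. It also calls for periodic survival status after treatment ends. Section 10 schedules examinations for patients who stop without progression, and it introduces its list of end-of-follow-up reasons with "Patients will remain in the follow-up period until any of the reasons below are satisfied". The four reasons are study completion, death, withdrawal of consent from follow-up, and loss to follow-up. Section 11 collects adverse events up to the safety visit and follows each serious event until it resolves or stabilizes.

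**The concern.** One list serves both for stopping the drug and for leaving the study. A site that removes a patient under the harm clause is told by Section 6 to end procedures, and by Sections 4, 10 and 11 to carry on with some of them. Both instructions cannot be followed. For the optional reasons the text permits study withdrawal without saying whether off-treatment follow-up continues.

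The reasons are related to the outcomes. Harm, severe allergic reaction, falling performance status and intercurrent illness all plausibly predict toxicity, progression or death. Ending observation for these reasons could remove events from the primary endpoint and censor PFS and OS in patients whose prognosis differs from that of those who remain. Two sites reading the protocol in good faith could also follow the same kind of patient differently.

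**Working it through.** The plan gives no figure on this point, so the check is mainly a comparison of passages, followed by arithmetic on the consequence.

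**1. Passages side by side for a patient removed under the harm clause**

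| Item | Section 6 read literally | Elsewhere |
|---|---|---|
| Safety visit | Ends with other procedures | Section 4: required, no exception by reason for stopping |
| AE collection | Ends | Section 11: continues to the safety visit |
| SAE follow-up | Ends | Section 11: until resolved or stable |
| Examinations off drug | End | Section 10 and Table of Assessments footnote c: at least three-monthly if not progressed |
| Survival status | Ends | Sections 4 and 10: continues; two failed contact attempts are needed before a patient counts as lost |
| Harm ends follow-up? | Yes | Section 10: not among the four reasons |

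For the optional reasons the left column is permitted rather than required.

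**2. Who is not exposed**

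Toxicity stops in Sections 7 and 8 end therapy only:

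- Table 7-1, footnote d: "If no recovery after a 4 week delay, treatment should be permanently discontinued unless subject is deriving clinical benefit".
- Table 8-2, footnote d: "Subjects requiring > 2 dose reductions should go off protocol therapy".
- Table 8-3 is worded the same way.
- Table 8-4 continues weekly transaminase measurement after one of its discontinuation rules.

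These patients move into the follow-up of Sections 4 and 10.

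**3. Effect on the primary rate**

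Inputs: 60 subjects and an expected rate of 45% (Section 12); everyone dosed at least once is in the safety analysis (Section 11); no replacement (Section 6). The plan's 90% interval of 0.341 to 0.564 is reproduced for 27/60 by the Wilson method with continuity correction. Its half-width is (0.564 - 0.341)/2 = 0.11; the plan states about 12%.

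A withdrawn patient with an unobserved first grade 3-5 event counts as event-free. One such patient changes 27/60 = 45.0% to 26/60 = 43.3%, that is 1/60 = 1.7 points.

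**4. Effect on OS (illustration under assumptions)**

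Assume exponential OS with a median of 6.4 months (the regorafenib arm of CORRECT, Section 1). Assign 5-30% of patients a Section 6 removal at a uniform time between 0.25 and 4 months. That is 60 x 0.05 = 3 to 60 x 0.30 = 18 patients, of whom about 2 to 14 are alive at that time. Vary their later death hazard relative to the others. Cells show the median in months with full follow-up, then the Kaplan-Meier median if they are censored at removal (400,000 simulated patients per cell).

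| Share assigned | Hazard x1 | x1.5 | x2 |
|---|---|---|---|
| 5% | 6.39 / 6.39 | 6.31 / 6.40 | 6.26 / 6.42 |
| 10% | 6.41 / 6.40 | 6.21 / 6.39 | 6.06 / 6.37 |
| 20% | 6.38 / 6.38 | 6.06 / 6.40 | 5.78 / 6.39 |
| 30% | 6.43 / 6.45 | 5.88 / 6.40 | 5.55 / 6.42 |

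With unchanged hazard there is no bias beyond simulation noise. With raised hazard the median is overstated by 6.40 - 6.31 = 0.09 to 6.42 - 5.55 = 0.87 months.

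**The case against.** The strongest reply is that the protocol already has a category for patients off drug but on study, only not in Section 6. Sections 7 and 8 take patients off therapy, and Sections 4 and 10 follow them. The harm clause speaks of the trial rather than the drug and does not name toxicity; if the trial itself is harmful, ending procedures is coherent. The one drug toxicity that Section 6 names is in the optional list, which lacks the reference to procedures. The event that prompted removal will usually be on record already, and Section 11 (Death) still requires reporting of deaths during the trial or within 30 days of the end-of-treatment visit.

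Most of this stands, and it limits the point. A reader might infer that everyone stopped for toxicity loses the safety visit and survival follow-up. The documents do not support that, because the dose-modification tables stop therapy without removing anyone from the study. Nor does worsening from grade 3 to grade 4 or 5 alter a grade 3-5 incidence, since the patient already counts; only the separate tabulations by grade could change. Accumulated grade 2 events do not by themselves lead to study withdrawal either: Table 7-1 (footnote c) and Table 8-2 answer them with interruption, reduction or stopping of therapy.

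What the reply does not remove is the contradiction itself. Section 7 makes Section 6 a list of treatment-stopping reasons, Section 6 attaches the end of procedures to one of them, and Section 10 does not recognize that reason as ending follow-up. The protocol does not say which passage takes precedence.

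**Conclusion.** The contradiction is real and should be corrected, but it is confined to patients removed under Section 6: those under the harm clause, where ending procedures is mandatory, and those under the optional reasons, where study withdrawal is permitted. It does not extend to toxicity stops in general.

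For the primary endpoint, the exposure is a first grade 3-5 event, mainly non-fatal, between the last dose and the safety visit. It costs 1.7 points per patient if all 60 are dosed. For OS, the bias depends on whether removed patients have a worse prognosis: none if they do not, and 0.09 to 0.87 months in the median under the assumptions shown. The upper end needs 30% of patients assigned to removal and a doubled hazard, and ordinary toxicity stops should not contribute to that share. PFS is exposed in the same way, although scan frequency after an early stop is already left to the treating physician. The documents give no rate of Section 6 removals, so neither the number affected nor the total bias can be derived.

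**What to change.** Reconcile the passages by dividing Section 6 into discontinuation of study treatment and withdrawal from the study. Leave the existing mandatory and optional triggers as they are, and leave untouched the subject's right to withdraw consent at any time from treatment, procedures or both.

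State that patients removed for harm or for an optional reason still have the Section 4 safety visit, the Section 11 adverse-event and serious-event follow-up, and the Section 10 follow-up. The exceptions are a Section 10 reason for ending follow-up, or withdrawal of consent by the subject. Point the Section 7 cross-reference at the treatment-discontinuation part.

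This changes who stays under observation, not when treatment stops. The cost is a wording amendment through the ethics review that Section 9 describes, plus a few more safety visits and survival contacts. The visits and the End of Study form already exist.

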### **Screen Failures/Withdrawals**

A subject who discontinues study participation prematurely for any reason is defined as a “withdrawal” if the subject has already been assigned to treatment or administered at least one dose of study drug.

A subject who, for any reason (e.g. failure to satisfy the selection criteria), terminates the study before the time point used for the definition of “withdrawal” (see above) is regarded as a “screen failure”.

### **Replacement**

No withdrawn subjects will be replaced.

